14.8 Other Efficacy Analyses

14.8.1 Individual Components of the Primary Endpoint

In addition to assessing the primary efficacy for subjects in MITT and PP analysis sets (Section 14.3.1), we will also assess the components of the primary efficacy endpoint (1) having CFB in blood bicarbonate ≥ 4 mEq/L and (2) having a blood bicarbonate in the normal range (22 to 29 mEq/L). The proportion (expressed as percentages) of MITT subjects with a component at each time point and at the end of treatment will be reported as described in the previous Section 14.3.1.

14.8.2 Categorical Change in Blood Bicarbonate

The proportions (expressed as percentages) of subjects with increases in their blood bicarbonate by ≥ 2 , ≥ 3 , ≥ 4 , ≥ 5 , ≥ 6 , and ≥ 7 mEq/L at each time point and at the end of treatment will be reported as described in the Section 14.3.1 for MITT subjects.

14.8.3 Change from Baseline in Biomarkers at Week 12

Efficacy variables, such as parathyroid hormone, serum pre-albumin, 25-hydroxy-vitamin D, urinary biomarkers of bone resorption (NTX and CTX), serum biomarkers of bone resorption (TRAP 5b, BSAP, and P1NP), urine renal biomarkers (aldosterone, uric acid, sulfate, and ET-1), and serum osteocalcin, all collected at baseline and once post baseline (at Week 12 Visit or early termination) will be analyzed using ANCOVA models similar to those described in Section 14.7, except for UAGT. Aldosterone, uric acid, sulfate, CTX, NTX, endothelin-1, and angiotensinogen are measured in the 24-hour urine collection.

For UAGT, geometric mean and 95% CI of the geometric mean, along with n, min and max, will be presented by treatment group and time point. The ANCOVA models will comprise the natural logarithm of the post baseline UAGT value as the dependent variable; treatment group as a fixed effect; and the natural logarithm of baseline value, the baseline eGFR, and baseline blood bicarbonate as continuous covariates. The geometric LS mean and two-sided 95% CI of the geometric LS mean from the ANCOVA model will be reported by treatment group. The geometric LS mean ratio (TRC101/placebo), 95% CI of the geometric LS mean ratio, and the p-value will also be provided. The geometric (LS) mean and its 95% CI will be obtained by exponentiating the (LS) mean and 95% CI on the natural log-scale.

14.8.4 Subgroup Analysis of Change in i-STAT Blood Bicarbonate Over Time

The treatment effect on i-STAT blood bicarbonate in subjects from different randomization strata (i.e., baseline blood bicarbonate \leq 18 versus $>$ 18 mEq/L and screening eGFR $<$ 30 versus \geq 30 mL/min/1.73m²) and dose titration status (i.e., receiving only 2 packets throughout entire study, up-titrated to 3 packets at any time, and down-titrated to 1 or 0 packet at any time) will be evaluated. The blood bicarbonate values, as measured by an i-STAT point-of-care device, along with change from baseline values, will be summarized by treatment and time point for each stratum and each titration status.

15 SAFETY ANALYSES

One of the study objectives is to assess the safety of TRC101. Safety will be evaluated by adverse events, clinical laboratory test results, vital signs, body weight, ECG findings, and physical examination and by the incidence of blood bicarbonate values > 30 mEqL. All analyses of the safety data will be performed using the safety analysis set, based on the actual treatment a subject received. All descriptive statistics (described in Section 10) will be presented by treatment group in the safety analysis set.

15.1 Safety Variables

Safety variables include:

1. AEs, SAEs and withdrawal of study drug due to AE
2. Having met the high bicarbonate dose interruption criterion (confirmed > 30 mEq/L) at any time during the Treatment Period
3. Laboratory test results
4. Vital signs
5. Body weight
6. Findings from 12-lead ECG

15.2 Adverse Events

TEAEs are defined in Section 11.4.1. All reported AEs (including non-TEAEs) will be listed. All TEAE summary tables will present the number and percentages of subjects reporting TEAEs. A summary of TEAEs by severity, seriousness, and relation to study drug will be tabulated. In addition, TEAEs will be summarized by MedDRA system organ class and preferred term. Subjects can have more than one TEAE per system organ class and preferred term. These summaries will include the following:

- All TEAEs
- TEAEs by worst severity
- Study drug related TEAEs
- Serious TEAEs
- TEAEs leading to study drug discontinuation (if any)
- Death (if any)

At each level of subject summarization, subjects are counted once if they reported at least one TEAE at that level. If a subject reported the same TEAE on multiple occasions, the highest severity (severe > moderate > mild) or study drug relationship (related > probable > possible > unlikely > unrelated) recorded for the event will be summarized. Each summary will be ordered by descending incidence of system organ class and preferred term within each system organ class, based on the Total column.

15.3 Incidence of High Bicarbonate

A summary table will be provided with number and percentage of subjects who had a bicarbonate > 30 mEq/L by time interval during the Treatment Period. The table will also include total number of subjects and total number of occurrences during the Treatment Period.

15.4 Clinical Laboratory Evaluation

Clinical laboratory test results from central laboratories (serum chemistry, hematology, coagulation, spot urine, 24-hour urine and urinalysis) will be summarized using descriptive statistics at baseline and at each scheduled post-baseline time point, unless otherwise specified. Changes from baseline will also be summarized by time point. Serum anion gap values from serum chemistry and urine anion gap from spot urine (Section 10.1.4) will be derived and summarized descriptively, in a similar way as collected laboratory results.

For urine albumin to creatinine ratio (from spot urine), the geometric mean and 95% CI of the geometric mean, along with n, min and max, will be presented by treatment group and time point. At post baseline time point, geometric mean fold rise and 95% CI of geometric mean fold rise will also be presented. The geometric mean and its 95% CI will be obtained by exponentiating the mean and 95% CI on the natural logarithm of urine albumin to creatinine ratio. The geometric mean fold rise and its 95% CI will be obtained by exponentiating the mean and 95% CI on the difference in natural logarithm of urine albumin to creatinine ratio from baseline.

Categorical display methods (e.g., frequencies, shift tables) for laboratory values over time may also be used, as appropriate. The number and percentage of subjects with any out of range chemistry and hematology values (i.e., above upper limit of normal, below lower limit of normal,

above a pre-specified level or below a pre-specified level) will be summarized by time point. Tricida chose these pre-specified levels for laboratory tests because they are more appropriate for the study population than normal ranges for healthy subjects (See Table 4 below).

Table 4 Pre-Specified Threshold Levels for Selected Laboratory Tests

Laboratory Category	Test Name	Pre-Specified Level
Chemistry	Sodium	< 132 mEq/L
Chemistry	Potassium	< 3.0, < 3.5, > 5.0, > 6.0 mEq/L
Chemistry	Blood bicarbonate	< 10, < 12, > 30, > 32 mEq/L
Chemistry	Creatinine	> 25% increase from baseline
Chemistry	eGFR (based on creatinine and Cystatin C)	< 10 mL/min/1.73m ² , < 15 mL/min/1.73m ² (among those with eGFR > 18 mL/min/1.73m ² at baseline) > 30%, > 40%, and > 50% decrease from baseline
Chemistry	Glucose	> 250 mg/dL
Hematology	Hemoglobin	< 9 g/dL
Hematology	Hematocrit	< 27%

Furthermore, in order to examine possible off-target effects of TRC101, the following descriptive summary statistics will be generated:

- CFB in serum potassium for the subset of subjects whose baseline serum potassium is >5.0 mEq/L, any time during the study treatment,
- CFB in serum phosphate for the subset of subjects whose baseline serum phosphate is >5.5 mg/dL, any time during the study treatment, and
- CFB in low density lipoprotein (LDL) for the subset of subjects whose baseline LDL is > 120 mg/dL, any time during the study treatment

Urinalysis results (other than pH and specific gravity), urine microscopic findings, and pregnancy test results will be listed, but not summarized.

From the 24-hour urine collection, the following data will be summarized and listed:

- Change in creatinine clearance (CrCL in mL/min), defined as [24-hour urine volume (mL) * 24 urine Cr (mg/dL)]/[Serum Cr (mg/dL)*1440]
- Change in 24-hour urea nitrogen excretion
- Change in 24-hour albumin excretion
- Change in 24-hour sulfate excretion
- Change in 24-hour uric acid excretion

All laboratory results will be listed. Laboratory results that are above or below normal limits will be flagged in the listings. In addition, laboratory results that meet or exceed the pre-specified levels (i.e., are above [or below as appropriated] the pre-specified levels as shown in the above table) will be flagged.

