12. Have liver enzyme (alanine aminotransferase [ALT], aspartate aminotransferase [AST]) or total bilirubin values $> 3 \times$ the upper limit of normal (ULN) at Screening based on central laboratory measurements.
13. Have a serum calcium ≤ 8.0 mg/dL at the Screening 1 Visit based on central laboratory measurement.
14. Have a serum potassium value < 3.8 mEq/L or > 5.9 mEq/L at the Screening 1 or Screening 2 Visit.
15. Have active cancer during the 1 year prior to Screening, other than non-melanoma skin cancer, or cancer that is currently being treated or will be treated during the study. Subjects with cancers that are being treated with hormonal therapy only may be permitted with approval of the Medical Monitor.
16. Have received any investigational medication during the last month (28 days or ≥ 5 half-lives [if known], whichever is longer) preceding the Screening 1 Visit.
17. Have used any of the following in the 14 days prior to the Screening 1 Visit: lanthanum carbonate, colesevelam, cholestyramine or sodium or calcium polystyrene sulfonate, calcium acetate, sevelamer, bixalomer, patiromer, and other polymeric binder drugs.
18. Have had a change in doses (including starting or stopping treatment) in the 2 weeks prior to the Screening 1 Visit or during Screening Period to the following: calcium-containing supplements, such as calcium carbonate and calcium citrate; antacids; H2-blockers; proton pump inhibitors. See [Section 5.9](#) for examples of specific drugs.
19. Have had a change in doses (including starting or stopping treatment) in the 4 weeks prior to the Screening 1 Visit or during Screening Period to the following:

sodium bicarbonate, potassium citrate, sodium citrate or other alkali therapy; diuretics; renin-angiotensin-aldosterone system [RAAS] inhibitors, such as angiotensin-converting enzyme [ACE] inhibitors, angiotensin II receptor blockers [ARBs], aldosterone antagonists [AAs], mineralocorticoid receptor antagonists [MRAs]; non-ophthalmic carbonic anhydrase inhibitors. See [Section 5.9](#) for examples of specific drugs.

Note: For diuretics, dose changes of up to \pm 50% relative to the average dose during the Screening Period are considered “stable”, and a dose change up to \pm 50% between the Screening 1 Visit and the Baseline Visit is considered “stable”.

20. Have a known allergy to placebo ([REDACTED]).
21. Inability to consume the study drug or otherwise comply with the protocol.

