15.5 Vital Signs

Descriptive statistics for blood pressure, heart rate, respiratory rate, and temperature, including baseline values and change from baseline values, will be summarized by treatment group and time

point. In addition, number and percentage of subjects with any out of range values (i.e., above a pre-specified level or below a pre-specified level) will be summarized by time point. Tricida chose these pre-specified levels for vital signs because they are more appropriate for the study population than normal ranges for healthy subjects. The pre-specified thresholds levels for vital signs (See Table 5 below).

Table 5 Pre-Specified Threshold Levels for Vital Signs

Vital Sign	Pre-Specified Level
Systolic blood pressure	< 100, > 190 mmHg, > 30% increase or decrease from baseline
Diastolic blood pressure	> 95 mmHg, > 20% increase or decrease from baseline
Heart rate	< 40, > 100 beats/min
Respiratory rate	< 10, > 20 breaths/minute, increase or decrease from baseline by ≥ 6 breaths/minute

All vital signs parameters will be listed. The listing will flag any vital signs that exceed the levels provided in the table above.

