15.6 Body Weight

Descriptive statistics for body weight measurements, including baseline values and change from baseline values, will be summarized by treatment group and time point. Body weight measurements will be listed along with vital signs.

15.7 12-lead Electrocardiograms

Listings will present ECG data, such as clinical interpretation of ECGs, ECG rhythm and assessments of heart rate (HR), and intervals of QRS, QT, and PR. The baseline cardiac rhythm will be descriptively summarized. Descriptive statistics for observed values and change from baseline at each time point will be presented for these 12-lead ECG interval and HR assessments. In addition, the number and percentage of subjects with any abnormal values (i.e. outside a pre-specified threshold) will be summarized by treatment and time point. The pre-specified levels of ECG QTc thresholds are consistent with FDA guidance (See Table 6 below).

Table 6 Pre-Specified Threshold Levels for ECG Parameters

ECG Parameter	Pre-Specified Level
PR	> 200 msec
QTcF	> 450, > 480 or > 500 msec, > 30 or > 60 msec increase from baseline
Heart rate	< 40, > 100 beats/minute

All ECG parameters will be listed. The listing will flag any results that outside the above levels provided in the table above.

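### Subjects beyond the Table 4–6 safety levels are counted only visit by visit: apart from bicarbonate above 30 no level has a committed per-subject on-treatment count, and about 17 of 39 levels mix new with entry abnormalities

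*SAP*

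**What the plan says.** SAP 15.4 sets levels for selected laboratory tests (Table 4) and states that subjects with values "above a pre-specified level or below a pre-specified level) will be summarized by time point". SAP 15.5 does the same for vital signs (Table 5), giving the "number and percentage of subjects with any out of range values" at each time point. SAP 15.7 does so for ECG (Table 6): "the number and percentage of subjects with any abnormal values (i.e. outside a pre-specified threshold) will be summarized by treatment and time point".

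The plan uses two refinements, once each. For bicarbonate above 30, SAP 15.3 adds: "The table will also include total number of subjects and total number of occurrences during the Treatment Period". For eGFR below 15, Table 4 restricts the count to subjects above 18 at baseline. Some levels are themselves changes from baseline, such as creatinine "> 25% increase from baseline".

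On entry values, Protocol 4.3 (criterion 14) excludes those who "Have a serum potassium value < 3.8 mEq/L or > 5.9 mEq/L at the Screening 1 or Screening 2 Visit", and SAP 15.4 plans a separate summary of "CFB in serum potassium for the subset of subjects whose baseline serum potassium is >5.0 mEq/L". Shift tables are mentioned in SAP 15.4 as optional, for laboratory values only. Under SAP 10, subjects without data leave the denominator of categorical summaries, and unscheduled or repeat values stay out of summary tables unless stated otherwise.

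**The concern.** A safety reader wants to know how many subjects in each arm crossed a level at least once on treatment and, where the level may already be exceeded at entry, how many did so newly. The planned tables give neither, apart from the two refinements above.

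Rare crossings are broken into visit counts of a few subjects. The per-subject total cannot be rebuilt from them, because the overlap between visits is not shown and the denominator changes as subjects leave. For a persistent trait such as a long PR interval, subjects abnormal at entry fill every row and new cases are hard to see. If these counts are chosen only after unblinding, they become post hoc. Safety is a stated objective, and SAP 15.4 sets out to look for off-target effects.

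**Working it through.** The plan gives no figure to reproduce here. The check is a count of levels, a bound, and illustrations with assumed rates.

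**1. Levels in Tables 4 to 6**, counting increase and decrease separately:

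| Class | Table 4 | Table 5 | Table 6 | Total |
|---|---|---|---|---|
| Change from baseline | 4 | 6 | 2 | 12 |
| Conditioned on baseline | 1 | 0 | 0 | 1 |
| Absolute, excluded by entry criteria | 8 | 1 | 0 | 9 |
| Absolute, possible at entry | 5 | 6 | 6 | 17 |
| Total | 18 | 13 | 8 | 39 |

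- The 9 excluded by entry criteria are potassium <3.0, <3.5 and >6.0, the four bicarbonate levels, eGFR <10, and systolic pressure >190.
- The 17 possible at entry are sodium <132, potassium >5.0, glucose >250, hemoglobin <9, hematocrit <27%, systolic <100, diastolic >95, respiratory rate <10 and >20, heart rate <40 and >100 (in both Table 5 and Table 6), PR >200, and QTcF >450, >480 and >500.
- The split is approximate. The potassium and systolic limits apply at screening and not on Day 1, and the eGFR limits are based on creatinine.

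**2. On-treatment visits (Protocol, Appendix 1).** Chemistry and vital signs have 7 (Weeks 1, 2, 4, 6, 8, 10, 12), ECG has 3 (Weeks 2, 6, 12) and hematology has 2 (Weeks 6, 12). Cystatin C eGFR has one post-baseline value, so nothing is split there.

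**3. What a by-visit rate says about the per-subject rate.** If a proportion p crosses at each of V visits, the per-subject rate lies between p (always the same subjects) and V × p (always different subjects). With independent visits it is 1 − (1 − p)^V. For V = 7:

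- p = 0.5%: 0.5% to 3.5%
- p = 1%: 1% to 7%; independent, 1 − 0.99^7 = 6.8%
- p = 2%: 2% to 14%

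For example, seven different TRC101 subjects, one per visit, show as 1/120 = 0.8% in each row but are 7/120 = 5.8% of the arm.

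**4. Illustration for potassium (assumed).** Mean 4.7–4.9, between-subject SD 0.4, within-subject SD 0.30–0.35, screening limits applied, TRC101 shift +0.2, 120 vs 90 subjects. The results are simulated and carry Monte Carlo error of a few points.

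- Already above 5.0 on Day 1: 25–38%.
- Above 6.0, Week 12 row: about 1–3 vs 0–1 subjects, with a 0–4% chance of Fisher p<0.05 (0–26% that any of the seven rows reaches it).
- Above 6.0, at least once on treatment: about 5–15 vs 1–5 subjects, with a chance of 14–42%.
- Above 5.0: Week 12 row 54–67%, against 53–73% for at-least-once among subjects not above 5.0 at baseline.

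**5. Illustration for a persistent ECG trait (assumed).** With 20% prevalence at entry and 10% vs 2% new cases among the rest, the planned count is 0.20 + 0.80 × 0.10 = 28% vs 0.20 + 0.80 × 0.02 = 22%, and the chance of p<0.05 is 16%. Counting only new cases gives 51–54%.

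**The case against.** The best case for the plan has four parts.

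- **Baseline is used.** A reader might infer that the tables ignore baseline altogether. They do not: 12 levels are changes from baseline, including those for creatinine, eGFR decline and QTcF increase, 1 is conditioned on baseline, and about 9 more are excluded by entry criteria. This stands and confines the mixing to about 17 levels. It does not touch the splitting, since a change level is also counted visit by visit.
- **Per-subject counts exist elsewhere.** Bicarbonate above 30, the protocol's laboratory-based safety endpoint, has one. Clinically significant new or worsening findings become adverse events and are counted once per subject. Values beyond a level are flagged in listings, and early-termination assessments are mapped into the tables (SAP 11.2). This stands in part. The adverse-event route depends on investigator judgement, which objective levels are meant to avoid, and listings give no comparison by arm.
- **The effect sizes are invented.** The Phase 1/2 study showed no trend suggesting an off-target effect on potassium or an effect on ECG intervals (Protocol 1.4.1.1). With 5% vs 2% new ECG cases, the new-case count has only an 8–12% chance of p<0.05. No test of these tables is planned. All of this stands, so the chances above measure only how visible a difference would be.
- **The new-case count is not always better.** For potassium above 5.0 it gains at mean 4.7 (70–73% vs 56–60% for the Week 12 row) but not at 4.9 (53–60% vs 54–63%). It drops the 25–38% already above the level, and 46–66% of eligible placebo subjects would count as new through fluctuation alone. This stands: such a count belongs beside the by-visit rows and should not replace them as the main display.

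**Conclusion.** The point holds in limited form. Apart from bicarbonate above 30, none of the levels in Tables 4 to 6 has a committed per-subject on-treatment count, and the by-visit rows cannot supply one. That gap matters most for rare levels. For about 17 of 39 levels, new and entry abnormalities are also counted together.

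Two stronger readings are not supported. One is that the comparison between arms is biased: randomization balances entry abnormality on average, so the effect is dilution and poor readability. The other is that a difference would necessarily be missed by visit and found per subject: for potassium above 6.0 the chance rises from 0–4% in the Week 12 row to 14–42%, but the latter overlaps the 0–26% for any row.

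The structural finding rests on the SAP text and the visit schedule alone. The potassium and ECG figures rest on assumed distributions and effects. No endpoint, alpha or sample size is affected.

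**What to change.** In SAP 15.4, 15.5 and 15.7, for each Table 4–6 level with more than one on-treatment value, add by arm the number (%) of subjects with at least one on-treatment value beyond it (Weeks 1–12), with the TRC101 minus placebo difference and 95% CI. For the absolute levels that can be present at entry, show the same count among subjects not beyond the level at baseline. Keep the by-visit counts, and keep the tables descriptive. State whether unscheduled and repeat values enter the new rows, since SAP 10 leaves them out by default.

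The cost is SAP wording and one or two extra rows per level from data already collected. The downside is the smaller denominator in the not-at-baseline row: about 25–38% of subjects lost for potassium above 5.0 under the assumed distribution.

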15.4.1 Summary of Change from Baseline in eGFR

The eGFR values are derived from the central laboratory serum creatinine using the CKD-EPI formula (Section 10.1.3). The eGFR values, CFB and percent CFB will be summarized descriptively by treatment group and time point. Graphs will be produced to show:

- Arithmetic mean \pm SE of CFB in eGFR by treatment group over time
- Arithmetic mean \pm SE of eGFR by treatment group over time

Because treatment of acidosis may increase muscle over time, a cystatin based eGFR will be used to evaluate eGFR changes independent of muscle mass changes. The eGFR derived from the central laboratory serum cystatin C values, using the CKD-EPI formula (Section 10.1.3), were measured at baseline and once post baseline. The eGFR values will be summarized at baseline and post baseline along with the CFB and percent CFB in eGFR will be summarized by treatment group.

15.4.2 Summary of Change from Baseline in Blood pH and Base Excess

This analysis will evaluate blood pH and base excess measured by the i-STAT point-of-care device. The blood pH and base excess values and CFB in blood pH and base excess will be summarized by treatment group and time point. All measurements from the i-STAT point-of-care device will be listed.

